- n. PRO assessments are not needed at the early withdrawal visit if PRO was already assessed within 2 weeks prior to the early withdrawal visit.
- o. Only applicable to subjects in the pharmacokinetic subgroup and subjects enrolled at a site with an on-site Fibroscan device.
- p. If a subject discontinues study treatment before the end of the 24-week treatment phase or, if applicable, the 24-week treatment extension phase (ie, Week 48 visit), a treatment withdrawal visit should be performed after which the subject will enter the 24-week follow-up, unless the subject withdraws consent. NA treatment (either ETV or TDF as per local practice) should be continued or, in case of JNJ-56136379 monotherapy, started at the time of early discontinuation of study treatment as per local treatment guidelines. An additional 24-week follow-up (as per local treatment guidelines), by their primary care physician outside of the study, is recommended after the 24-week follow-up phase in the study, for subjects who do not continue or start NA treatment at Week 24 or 48. Subjects who withdraw consent will be offered an optional safety follow-up visit.
- q. HBcrAg and HBV RNA samples may be batched and only selected samples may be tested. Samples can be used for assessment of other serologic/virologic markers of HBV.
- r. Subjects withdrawing consent during the follow-up period will be offered an optional safety follow-up visit.
- s. For female subjects on a hormonal contraceptive regimen (regardless of type and route of administration), the start of contraceptive administration at the last initiated cycle (if applicable for the type of contraception) will be documented in the eCRF.
- t. All follow-up study visits are to be scheduled relative to the last dose of JNJ-56136379 and are to occur at the end of Weeks 2, 4, 12, and 24. The visit window is  $\pm 2$  days of the protocol-specified date at Weeks 2-4,  $\pm 5$  days of the protocol-specified date through Week 24.

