Treatment with JNJ-56136379 may lead to emergence of viral variants with reduced susceptibility or resistance to JNJ-56136379. Based on pre-clinical data, these variants remain susceptible to TDF and ETV but might affect treatment options with CAMs in the future.

As of 6 February 2019, virological breakthrough, as defined by the protocol (ie, confirmed on-treatment HBV DNA increase  $>1 \log_{10}$  from nadir level or confirmed on-treatment HBV DNA level  $>200$  IU/mL in subjects who had HBV DNA level below the LLOQ of the HBV DNA assay), was observed in 5 out of the 28 subjects on JNJ-56136379 75 mg monotherapy. In addition, there were 2 subjects who met the virological breakthrough threshold but, due to the change of treatment, the virological breakthrough could not be confirmed. The virological breakthrough in these subjects is expected to be associated with viral resistance to JNJ-56136379. An HBV DNA decline was observed in these subjects upon initiation of NA treatment confirming pre-clinical data showing that viral variants resistant to JNJ-56136379 remain susceptible to NA treatment.

Given the virological breakthroughs observed in the JNJ-56136379 75 mg monotherapy arm (Treatment Arm 1), this treatment arm was discontinued early per Protocol Amendment 4. All subjects were to stop further dosing with JNJ-56136379 75 mg, start treatment with NA, and enter the post-treatment follow-up phase (Schedule 1).

In addition, per Protocol Amendment 4, the duration of treatment with JNJ-56136379 250 mg monotherapy has been limited to a maximum of 24 weeks (see Section 6.1). As an additional precautionary measure to safeguard the subjects, a stringent futility rule has been implemented in the JNJ-56136379 250 mg monotherapy arm (see Section 6.2).

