
 
To evaluate efficacy in terms of HBsAg (in all subjects) or HBeAg (in HBeAg-positive subjects only) seroclearance and/or seroconversion.
 
	
 
Proportion of subjects with HBsAg or HBeAg seroclearance (defined as HBsAg or HBeAg negativity, respectively, based on the assay used) during study treatment and follow-up.
 
Proportion of subjects with HBsAg or HBeAg seroconversion (defined as HBsAg or HBeAg negativity and anti-HBs or anti-HBe antibody positivity, respectively) during study treatment and follow-up.
 

 
To evaluate the frequency of subjects with biochemical response.
 
	
 
Proportion of subjects with ALT improvement and normalization during study treatment and follow-up.
 

 
To evaluate the frequency of HBV virological breakthrough.
 
	
 
Proportion of subjects with virological breakthrough during study treatment defined as confirmed on-treatment HBV DNA increase by <math>>1 \log_{10}</math> from nadir level or confirmed on-treatment HBV DNA level <math>>200</math> IU/mL in subjects who had HBV DNA level below the lower limit of quantification (LLOQ) of the HBV DNA assay.
 

 
To evaluate the potential effect of JNJ-56136379 on the pharmacokinetics of NA when coadministered.
 
	
 
Pharmacokinetics of NA when administered as monotherapy or when coadministered with JNJ-56136379.
 

Objectives	Endpoints

 
To evaluate the pharmacokinetics of JNJ-56136379 when administered as monotherapy.
 
To evaluate the potential effect of NA on the pharmacokinetics of JNJ-56136379 when coadministered.
 
To assess changes in the HBV genome sequence.
 
	
 
Pharmacokinetics of JNJ-56136379 when administered as monotherapy or when coadministered with an NA.
 
Emergence of treatment-associated mutations during study treatment and follow-up.
 

Exploratory	

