10. The subject has a QTcF prolongation (defined as a QTcF value of  $>500$  ms, or an increase from baseline of  $>60$  ms) at any given time point (confirmed by repeat ECG).
11. The subject has at Week 4  $<1 \log_{10}$  IU/mL decline in HBV DNA from baseline, confirmed by retesting at the Week 8 visit (treatment-naïve only).
12. The subject has confirmed HBV virological breakthrough (ie, confirmed on-treatment HBV DNA increase by  $>1 \log_{10}$  IU/mL from nadir level or confirmed on-treatment HBV DNA level  $>200$  IU/mL in subjects who had HBV DNA level  $<$  LLOQ of the HBV DNA assay).
13. The subject requires treatment with any of the disallowed medications listed in Section 8.

Retesting for confirmation of the above-mentioned abnormal safety parameters (ie, not applicable to criteria 11 and 12 listed above) should take place within 72 hours after the initial results become available and may require an unscheduled visit.

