**Table 1: Construction of phases**

Analysis phase	Analysis Period	Start date	End date
Screening (phase 1)		The date of signing the informed consent	1 day before the first study agent intake
Treatment (phase 2)	Initial Treatment	Date of first study agent intake	- If not included in the treatment extension°: Date of last study agent intake + 5 days*

Analysis phase	Analysis Period	Start date	End date
	(period 1)		- If included in the treatment extension o : Date of Week 24 study agent intake+5 days #
	Treatment Extension (period 2)	End of the initial treatment period + 1 day	Date of last study agent intake + 5 days*
Follow-up (phase 3)		End of the treatment phase +1 day	Trial termination date (date of last contact) or cut-off date for an interim analysis, whichever comes first

o depending on the answer in the FA dataset: FAOBJ = " WILL THE SUBJECT CONTINUE TREATMENT IN TREATMENT EXTENSION PHASE?" and whether actually treatment was extended in the EX dataset.

\* or study termination date (date of last contact) or cut-off date for an interim analysis, whichever comes first.

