### 5.2.1 Parameter Definitions

The following parameters will be derived as follows:

*Viral breakthrough during 24 weeks of treatment (all subjects), during 48 weeks of treatment (subject with treatment extension) and during NA follow up for all subject who switch to NA-treatment during follow-up:*

HBV virological breakthrough is defined as having a confirmed on-treatment HBV DNA increase by  $>1$  log10 from nadir level (lowest level reached during 24/48 weeks treatment) or a confirmed on-treatment HBV DNA level  $>200$  IU/mL in subjects who had HBV DNA level below the lower limit of quantification (LLOQ) of the HBV DNA assay.

The proportion of subjects with a viral breakthrough is defined as follows:

---

- 0 (No) = subject has not had a viral breakthrough (see definition above) up to the considered time point
- 1 (Yes) = subject has a viral breakthrough at the considered time point or has had a viral breakthrough before (regardless of the HBV DNA result at the considered time point)
- 2 (No: ongoing): subject has not had a viral breakthrough (see definition above) up to the last time point but is still ongoing (only for interim analysis)

Confirmed means that the criterion should be fulfilled at 2 or more consecutive time points or at the last observed time point on-treatment. On-treatment means in the treatment phase, except for the baseline record.

The proportion of subjects with a viral breakthrough during initial 24- or 48-weeks treatment but still on NA Treatment (Yes / No)

Note: For Viral breakthrough during NA follow up, only subject on NA treatment will be include in the denominator.

*Viral relapse* is defined in the follow-up phase as follows:

- 1 (Yes) = viral relapse: confirmed  $\geq 2000$  IU/mL quantifiable.
- 0 (No) = no viral relapse: at least one post-treatment measurement available and not a viral relapse
- 2 (Not applicable) = no post-treatment HBV DNA measurements available
- 3 (No: ongoing) = no viral relapse: at least one post-treatment measurement available and not a viral relapse but still ongoing (only for interim analysis)

Confirmed means that the criterion should be fulfilled at 2 or more consecutive time points or at the last observed time point.

Note: viral relapse will only be assessed for those subjects who at the actual end of treatment have HBV DNA  $< 20$  IU/ml detectable/ undetectable.

*Biochemical relapse* is defined in the follow-up phase as follows:

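### The SAP labels a criterion met only at the last observed value as confirmed breakthrough or relapse, although the protocol classes two such 75 mg monotherapy subjects as unconfirmed

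*SAP*

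**What the plan says.** Protocol section 2.1 lists breakthrough as a secondary endpoint: "Proportion of subjects with virological breakthrough during study treatment defined as confirmed on-treatment HBV DNA increase by" more than 1 log10 from nadir, with a second limb (above 200 IU/mL, also confirmed) for subjects who had been below the LLOQ. It makes no exception for a last value. Protocol section 10.2 sets a 72-hour retest for abnormal safety parameters but excludes breakthrough from it ("ie, not applicable to criteria 11 and 12 listed above"), so no retest interval is given.

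Protocol section 1.3.4 shows the definition in use. As of 6 February 2019, breakthrough "was observed in 5 out of the 28 subjects on JNJ-56136379 75 mg monotherapy". The section then describes a further group, kept out of that count: "there were 2 subjects who met the virological breakthrough threshold but, due to the change of treatment, the virological breakthrough could not be confirmed".

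SAP section 5.3, under Parameter Definitions (numbered 5.2.1 in the text), repeats the two limbs and then adds: "Confirmed means that the criterion should be fulfilled at 2 or more consecutive time points or at the last observed time point on-treatment". It continues: "On-treatment means in the treatment phase, except for the baseline record". SAP Table 1 ends that phase at "Date of last study agent intake + 5 days", or at the interim cut-off or study termination if earlier. The same Parameter Definitions text lets the last observed time point stand as confirmation for viral relapse and for biochemical relapse. Protocol section 2.1 requires confirmed HBV DNA increases and a confirmed ALT value for its relapse endpoints.

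**The concern.** The two documents give the same word different meanings. A subject whose only over-threshold value is the last one on treatment is unconfirmed in the protocol's own account and confirmed in the SAP's tables. The SAP does not flag the change. Its coding (No, Yes, No but ongoing) has no category in which such a subject could be seen.

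The definition is used widely. It feeds on-treatment failure in SAP 5.3, time to breakthrough in Table 5, the group proportions in the secondary analysis, and the choice of subjects for the sequencing tables at breakthrough in section 7. Readers would take the SAP rate as the protocol's confirmed endpoint when it may include unconfirmed values.

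Interim analyses raise a second problem. An ongoing subject's latest visit is the last observed time point, so any single high value there qualifies.

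**Working it through.** **Inputs**

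- Confirmed breakthroughs, 75 mg monotherapy, 6 February 2019: 5 of 28 (Protocol 1.3.4).
- Over the threshold but not confirmed: 2 (same section).
- Interval method: Clopper-Pearson 95% (SAP, Secondary Analysis). For x of n, the lower limit is the 2.5% quantile of Beta(x, n − x + 1) and the upper limit is the 97.5% quantile of Beta(x + 1, n − x).

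**1. The protocol's figure.** The 5 of 28 is an observed count and cannot be re-derived without subject-level HBV DNA. It gives 5/28 = 17.9% (6.1 to 36.9).

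**2. Effect of the last-value clause on the 2 unconfirmed subjects**

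| Unconfirmed subjects whose over-threshold value is the last on-treatment record | Count | Rate (95% CI) |
|---|---|---|
| 0 | 5/28 | 17.9% (6.1 to 36.9) |
| 1 | 6/28 | 21.4% (8.3 to 41.0) |
| 2 | 7/28 | 25.0% (10.7 to 44.9) |

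The largest change is 2 subjects: 2/28 = 7.1 percentage points, a ratio of 7/5 = 1.4. With the planned arm size of 30 as denominator, the same counts would give 5/30 = 16.7% and 7/30 = 23.3%.

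**3. Why the result is a range.** The clause applies only if the over-threshold value is the subject's last record in the SAP treatment phase. That phase runs 5 days past the last study agent intake, and SAP section 2 defines study agent as JNJ-56136379 or placebo, so starting NA does not extend it. For early stoppers "a treatment withdrawal visit should be performed after which the subject will enter the 24-week follow-up", and HBV DNA is on that visit's schedule. A below-threshold sample within the 5 days, possibly after NA had begun, would be the last record and the subject would not count. The protocol gives no dates or values for the 2 subjects. Its attribution to the change of treatment makes 7 the most plausible count, but does not establish it.

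**4. Interim behaviour.** Take an ongoing subject with low values, one value over the threshold just before the cut-off, and a low value at the next visit. At the interim the high value is the last on-treatment record, so the code is Yes. At the next analysis it is neither the last record nor one of two consecutive ones, so the code becomes No. Yet the SAP's coding says that a breakthrough, once reached, stays Yes whatever the later HBV DNA result.

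**5. Relapse.** For re-treatment, Protocol section 6.4 speaks of an original test and a corresponding confirmation test, preferably at least 4 weeks apart. Confirmation there means a second test. The SAP's relapse definitions accept one value if it is the last.

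**The case against.** The strongest reply is that the protocol's endpoint table does not define confirmed, that section 11 leaves details to the SAP, and that the SAP fills the gap with a conservative, prespecified rule. When treatment changes straight after a rise, no second on-treatment value can exist. Counting the case as a failure is defensible, and a strict rule can undercount. This stands as a reason to keep last-value cases visible. It does not justify calling them confirmed, because the protocol has already classified such cases as not confirmed.

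It is also true that individual values will be listed, that an isolated blip at an interim corrects itself once later data arrive, and that this is a secondary endpoint in an exploratory study without formal testing. These points limit the consequences.

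A reader might infer more than the documents support:

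- **That the SAP result will be 7 of 28.** Neither document states this. It is an upper bound on a snapshot; dosing in the arm stopped afterwards, and numerator and denominator may both change.
- **That the rule biases comparisons between arms, because Arm 1 was cut short.** Every subject with on-treatment data has exactly one last on-treatment value, truncated or not, so the clause adds one opportunity per subject in every arm. No differential effect is shown.
- **That the rule bears on the closure of Arm 1.** The protocol's account of that decision uses its own definition and reports the 2 unconfirmed cases separately.
- **That a value just above 50 IU/mL is enough.** This needs a target-not-detected nadir imputed as 5 IU/mL; a detected nadir imputed as 15 would need about 150. It also needs the 1 log10 limb to apply to subjects already below the LLOQ, who have a separate 200 IU/mL limb. That is a question of imputation and nadir, separate from confirmation.

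**Conclusion.** The concern holds in limited form. The SAP reports as confirmed a class of values that the protocol reports as unconfirmed. For the 75 mg monotherapy arm at 6 February 2019 the supported range is 5 to 7 of 28, at most 7.1 percentage points above the protocol's rate, with wide and overlapping intervals. The upper end assumes that both unconfirmed values were the last HBV DNA record in the SAP treatment phase. The discrepancy in definition does not depend on the exact count. The interim problem follows from the SAP's text alone, and the relapse definitions have the same defect. The documents give no counts from which to size either.

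**What to change.** In SAP section 5.3:

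- Define confirmed as the criterion met at two or more consecutive assessments, scheduled or unscheduled. Referring to assessments matters because SAP section 2.3 keeps only one measurement per analysis window for tabulations, which could hide a retest.
- Add a separate category: criterion met at the last observed value only, unconfirmed.
- Show the combined rate (confirmed plus last-value-only) as a sensitivity analysis.
- At interim analyses, keep ongoing subjects with a single last value out of the confirmed Yes category.
- Make the same changes for viral and biochemical relapse; clinical viral relapse, which is built from these two, will follow.

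The cost is SAP wording and an extra row in the affected tables. No data collection changes, and the protocol's treatment discontinuation criteria are not touched. The drawback is that the headline rate no longer includes subjects whose treatment ended before a second value was possible. They remain visible in the separate row and in the sensitivity analysis.

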
 
To explore changes in the severity of liver disease.
 
To explore the relationship of pharmacokinetics with selected pharmacodynamic (PD) parameters of efficacy and safety.
 
To explore efficacy in terms of changes in HBV RNA and hepatitis B core-related antigen (HBcrAg) levels.
 
To explore the effect of viral and host baseline factors on efficacy and safety.
 
To explore the effect of baseline amino acid substitutions in the HBV genome on efficacy.
 
To explore the impact of HBV treatment on symptoms, functioning, and health-related quality of life (HRQoL) using patient-reported outcomes (PROs).
 
To explore the potential effect of JNJ-56136379 on the pharmacokinetics of ethinyl estradiol (EE) when coadministered.
 
	
 
Changes in fibrosis (according to Fibroscan liver stiffness measurements) at end-of-treatment (EOT) and end of follow-up versus baseline.
 
Relationship of various pharmacokinetic parameters with selected efficacy and safety endpoints.
 
Changes from baseline in HBV RNA and HBcrAg levels during study treatment and follow-up.
 
Impact of viral and host baseline factors on different efficacy and safety parameters.
 
Impact of baseline HBV sequence variations on efficacy parameters.
 
Impact of HBV treatment on symptoms, functioning, and HRQoL using PROs, ie: 
 
5-level EuroQol 5-Dimension (EQ-5D-5L) Visual Analog Scale score and Index Score;
 
Hepatitis B Quality of Life Instrument (HBQOL).
 
Medical Outcomes Study Cognitive Functioning Scale-Revised (MOS-CFS Cog-R);
 
Short Form 36 version 2 (SF-36v2) 8 Domain Scores/Subscales, Physical Component Summary and Mental Component Summary scores.
 
 
 
Pharmacokinetics of EE when coadministered with JNJ-56136379.
 

The following objectives and endpoints are applicable to the treatment extension phase only.

Objectives	Endpoints

 
• To evaluate the proportion of subjects able to complete all treatment at Week 48.
 
	
 
• Proportion of subjects meeting the treatment completion criteria as outlined in Section 6.3.
 

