
 
• To evaluate the frequency of sustained off-treatment response.
 
	
 
• Proportion of subjects with sustained reduction/suppression and/or sero-clearance considering single and multiple markers such as HBsAg, HBeAg, HBV DNA and ALT levels at FU Week 12, 24 and 48.
 

 
• To evaluate the frequency of virologic and clinical relapse after EOT.
 
	
 
• Proportion of subjects with virologic relapse defined as confirmed post-treatment increases in HBV DNA <math>>2,000</math> IU/mL after having met the treatment completion criteria.
 
• Proportion of subjects with clinical relapse defined as confirmed post-treatment increases in HBV DNA <math>>2,000</math> IU/mL after having met the treatment completion criteria, in association with confirmed ALT value <math>>2 \times</math> ULN.
 

 
• To evaluate the proportion of subjects requiring NA re-treatment during follow-up.
 
	
 
• Proportion of subjects who meet the re-treatment criteria as outlined in Section 6.4.
 

 
• To evaluate the efficacy of NA re-treatment during follow-up.
 
	
 
• Proportion of subjects with decline in HBV DNA, ALT and/or HBsAg levels after re-start of NA treatment during follow-up.
 

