- 1 (Yes) = biochemical relapse: confirmed  $ALT > 2 * ULN$ .
- 0 (No) = no biochemical relapse: at least one post-treatment measurement available and not a viral relapse
- 2 (Not applicable) = no post-treatment ALT measurements available

---

- 3 (No: ongoing) = no biochemical relapse: at least one post-treatment measurement available and not a biochemical relapse but still ongoing (only for interim analysis)

Confirmed means that the criterion should be fulfilled at 2 or more consecutive time points or at the last observed time point.

Note: biochemical relapse will only be assessed for those subjects who at the actual end of treatment have  $ALT \leq ULN$ .

*Clinical viral relapse is defined as follow:*

- 1 (Yes) = if both viral and biochemical relapse
- 0 (No) = otherwise and not ongoing
- 2 (Not applicable) = no post-treatment measurements available
- 3 (No: ongoing) not both viral and biochemical relapse but still ongoing (only for interim analysis)

Note: clinical viral relapse will only be assessed for those subjects who at the actual end of treatment have  $HBV\ DNA < 20\ IU/ml$  detectable/ undetectable and  $ALT \leq ULN$ . *Seroconversion of HBsAg (all subjects) / HBeAg (positive subjects) at week 24 of the treatment and at week 48 of the treatment (only subjects with treatment extension)* is defined as a confirmed loss of HBsAg/HBeAg at week 24/48 of the treatment. Loss is defined as a baseline HBeAg /HBsAg (qualitative) with a "REPEAT REACTIVE, CONFIRMED" or "POSITIVE" result and a post-baseline assessment with a "NEGATIVE" result.

*Seroconversion of HBsAg (all subjects) /HBeAg (positive subjects) at week 24 of the treatment and at week 48 of the treatment (only subjects with treatment extension)* is defined as:

- Use the selected time point for the week 24 or 48 visit as described in 2.3.
- A confirmed loss of HBsAg/HBeAg at week 24/48-of the treatment (i.e. seroclearance)
- and an appearance of Anti-HBs/Anti-HBe.

Loss is defined as a baseline HBeAg /HBsAg (qualitative) with a "REPEAT REACTIVE, CONFIRMED" or "POSITIVE" result and a post-baseline assessment with a

---

"NEGATIVE" result. Appearance is defined as a baseline Anti-HBs/ Anti-HBe (qualitative) with a "NEGATIVE" result and a post-baseline assessment with a "POSITIVE" result. Both criteria should be fulfilled.

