### 5.2.1 Secondary Analysis

- Descriptive statistics of the actual values (original unit and log10 transformed values) and the change from baseline (log10 transformed values) over time for qualitative viral activity parameters according to the specification described in section 2.6 will be included.
- LS means (SE) of change from baseline (and 95% confidence interval) for qualitative viral activity parameters per time point and overall based on log10 transformed values will be analyzed by subject population and part using mixed effects model for repeated measures similar as described in section 5.2.1.1.. Also P-values for treatment, time, their interaction and overall will be added.
- LS means (SE) of change from baseline (and 95% confidence interval) for qualitative viral activity parameters (except for HBeAg) per time point and overall based on log10

---

transformed values will be analyzed by subject population, part and by HBeAg status using mixed effects model for repeated measures similar as described in section 5.2.1.1. Also P-values for treatment, time, their interaction and overall will be added.

- A tabulation of the proportion of subjects with virological breakthrough during 24 week treatment and during 48 week treatment (only subjects with treatment extension) will be included.
- A tabulation of the proportion of subjects with viral relapse will be provided. For the purpose of the analysis, the denominator will only include those subjects with values Yes and No.
- Descriptive statistics of the maximum decrease from baseline ( $\log_{10}$  transformed values) over time for qualitative viral activity parameters according to the specification described in section 2.6 will be included.
- A tabulation of the status change from baseline at week 24 and at week 48 (only subjects with treatment extension) will be displayed by viral activity parameter.
- A tabulation of the proportion of subjects who meet the criteria of response categories per time point defined in section 5.3.1 will be displayed by viral activity parameter.
- A tabulation of the proportion of subjects who meet the criteria of response categories per period defined in section 5.3.1 (additional information in the table) will be displayed by viral activity parameter.
- A tabulation of the qualitative result of HBeAg and HBsAg per timepoint (week 24 and week 48) will be included.
- A tabulation of the biochemical response per time point will be included.

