- All individual values will be presented in subject listings: (1) including all subjects, (2) including subjects with viral breakthrough during 24 weeks or 48 weeks treatment (only subjects with treatment extension) and (3) including subjects with viral relapse.
- Mean (+/- SE) plots of the actual ( $\log_{10}$  transformed) values for all viral activity parameters will be presented by parameter.
- Mean (+/- SE) plots of the change from baseline for all viral activity parameters will be presented by parameter.
- A plot representing all actual ( $\log_{10}$  transformed) values of all viral activity parameters for each subject will be included. One graph per subject.
- The actual ( $\log_{10}$  transformed) values over time are plotted per the viral activity parameter. Each line will represent one subject.
- The change from baseline ( $\log_{10}$  transformed values) over time are plotted per the viral activity parameter. Each line will represent one subject.

---

The proportion of subjects for the secondary categorical endpoints below will be categorized by treatment group, HBeAg status and overall (pool HBeAg status) during study treatment and follow-up and where appropriate the difference between proportions and Clopper-Pearson 95%CIs may be calculated using a chi-square test of equal proportions.

- The proportion of subjects with a viral breakthrough
- The proportion of subjects with HBsAg seroclearance
- The proportion of subjects with HBsAg seroconversion
- The proportion of subject with viral relapse
- The proportion of subjects with HBsAg reduction
- The proportion of subjects with HBeAg reduction
- The proportion of subjects with HBVDNA reduction
- The proportion of subjects with HBV RNA reduction
- The proportion of subjects with biochemical relapse
- The proportion of subjects with clinical viral relapse

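### The SAP selects subjects for viral and clinical relapse on suppression at end of treatment, not on having met the treatment completion criteria, so the protocol's off-treatment relapse rate can be understated.

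*SAP*

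**What the plan says.** **Protocol 2.1** introduces the relapse objectives with "The following objectives and endpoints are applicable to the treatment extension phase only". Virologic relapse is a confirmed post-treatment HBV DNA rise above 2,000 IU/mL "after having met the treatment completion criteria". Clinical relapse is the same event in association with a confirmed ALT above 2 x ULN. Under **Protocol 6.3** the completion criteria are judged at Week 40 and confirmed at Week 44, and subjects who meet them stop all treatment after Week 48. Raised ALT is allowed if the investigator does not attribute it to HBV activity.

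**SAP 5.3, Parameter Definitions** (printed as 5.2.1) defines viral relapse in the follow-up phase as confirmed HBV DNA of 2000 IU/mL or more. Its population note reads "viral relapse will only be assessed for those subjects who at the actual end of treatment" have HBV DNA below 20 IU/mL. For the clinical endpoint, "clinical viral relapse will only be assessed for those subjects who at the actual end of treatment have" that result and ALT at or below ULN.

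**SAP 5.3, Secondary Analysis** (also printed as 5.2.1) says of the viral relapse table that "the denominator will only include those subjects with values Yes and No". The list of proportions, which includes viral and clinical relapse, "will be categorized by treatment group, HBeAg status and overall (pool HBeAg status) during study treatment and follow-up".

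**SAP 2.3, Table 1** ends the treatment phase at "Date of last study agent intake + 5 days", so the end follows JNJ-56136379 or placebo and not NA.

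**The concern.** The completion criteria exist to explore finite treatment, and relapse after stopping is the safety side of that question. The protocol's denominator is the people who stopped everything. The SAP's denominator is the people who were suppressed when the study agent ended, many of whom stay on or start NA. Subjects kept on NA are not expected to rebound above 2,000 IU/mL, so each one adds to the denominator and rarely to the numerator. Stopping would then look safer than it is. The SAP's entry conditions also remove some subjects who did stop, which changes the endpoint in a second way.

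**Working it through.** The documents state no relapse rate and no count of subjects expected to stop treatment, so there is no figure to reproduce. The check compares the definitions.

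**Step 1: does follow-up include subjects on NA?** Yes. Table 1 starts follow-up the day after the treatment phase ends, and SAP section 2 defines study agent as JNJ-56136379 and placebo only. SAP 2.3 then names two follow-up types. Treatment-free subjects met Protocol 6.3. NA follow-up subjects did not, and they start or continue NA.

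**Step 2: who enters each endpoint?** This assumes at least one post-treatment measurement is available.

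| Subject | Protocol relapse endpoints | SAP viral relapse | SAP clinical relapse |
|---|---|---|---|
| Met 6.3; HBV DNA <20 and ALT <=ULN at EOT | in | in | in |
| Met 6.3; HBV DNA <20, ALT >ULN not attributed to HBV | in | in | out |
| Met 6.3 at Weeks 40/44; HBV DNA >=20 at EOT | in | out | out |
| Did not meet 6.3, on NA; HBV DNA <20 at EOT | out | in | in if ALT <=ULN |
| Did not meet 6.3; HBV DNA >=20 at EOT | out | out | out |

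Row 4 is the source of dilution. Rows 2 and 3 are losses that no split by follow-up type repairs.

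**Step 3: could row 4 be large?** Each part plans about 40 virologically suppressed subjects, who enter on NA with HBV DNA below 60 IU/mL. Stopping requires HBV DNA below LLOQ, HBeAg negativity, HBsAg of 500 IU/mL or less and an HBsAg decline of at least 1 log10. Those who stop are therefore a restricted subset of those suppressed.

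**Step 4: size, under assumptions only.** Let D be subjects suppressed at EOT, m those of them who stopped all treatment, r the relapse rate off treatment and q the rate of confirmed HBV DNA >=2000 IU/mL on NA. A display not split by follow-up type gives

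pooled rate = [m x r + (D - m) x q] / D.

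The protocol's rate is r. With q near 0 the pooled rate is about r x m/D.

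- Small example: D = 25, m = 5, 3 relapses, q = 0. Protocol 3/5 = 60%; pooled 3/25 = 12%. With m from 2 to 10, D/m runs from 25/2 = 12.5 to 25/10 = 2.5.
- Planned size: 2 x 110 = 220, with 80% assumed suppressed, so D = 176; 10% of these stop, so m = 18; r = 60%, q = 0. Pooled = 18 x 0.60 / 176 = 10.8/176 = 6.1%, against 60%.
- Range: 60 to 95% suppressed, 2 to 25% of these stopping, r = 40 to 80%, q = 0 to 2%. Lowest: 4 x 0.40 / 209 = 0.8%. Highest: (33 x 0.80 + 99 x 0.02) / 132 = 28.38/132 = 21.5%.

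Only the planned size comes from the documents.

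**The case against.** A reader might infer that the off-treatment relapse rate will be diluted, and that every Schedule 1 subject on NA is counted. The documents do not support either reading.

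- **A split is provided for.** SAP 2.3 says follow-up types will be presented in the efficacy part, and the opening of SAP 5 has virology and serology analysed by follow-up type when applicable. In a table split that way the treatment-free stratum is not diluted.
- **A treatment-free definition exists.** SAP 5.3 defines post-treatment failure in treatment-free follow-up, limited to subjects who completed 48 weeks and met the criteria, with confirmed HBV DNA above 2000 IU/mL. That matches the protocol's virologic relapse in population and threshold.
- **Many Schedule 1 subjects are excluded.** Those with HBV DNA of 20 IU/mL or more at EOT, including many breakthroughs, fail the SAP note. Clinical relapse also needs ALT at or below ULN.
- **The protocol delegates detail.** Protocol 11.3.3 leaves the categorisation of relapse to the SAP, and the protocol's association of ALT with HBV DNA has no time window.
- **End of treatment is ambiguous.** SAP section 2 includes NA in Treatment, so the phrase could mean the end of NA.
- **Consequences are bounded.** No formal testing is planned, subjects with viral relapse are listed individually, and >=2000 differs from >2,000 only at exactly 2000.

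The first three points stand and limit the claim: dilution is possible, not certain. They do not close the gap. The relapse bullets do not name follow-up type and ask for an overall figure, although breakthrough during NA follow-up has its own denominator note. The treatment-free failure definition is not in the list of proportions and does not cover clinical relapse. Delegated detail does not extend to replacing the protocol's population. On the ambiguity, Table 2 derives EOT as the last visit in the treatment phase, which fits the study-agent reading better. The threshold difference is trivial in effect, but it leaves two viral relapse definitions in one SAP section.

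**Conclusion.** Wrong as written. The SAP's population for viral and clinical relapse is not the protocol's. It is broader because it admits suppressed subjects on NA. It is narrower because it drops subjects who stopped all treatment but had HBV DNA of 20 IU/mL or more at EOT and, for clinical relapse, those with ALT above ULN not attributed to HBV. Any relapse proportion not split by follow-up type can understate relapse after stopping; a split removes that problem but not the exclusions.

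No trial-specific dilution can be computed. The 60% against 12% example, and the 0.8 to 21.5% pooled range for off-treatment rates of 40 to 80%, rest on assumed counts and rates. The conclusion about definitions does not depend on them; it rests on reading end of treatment as the end of study agent. Biochemical relapse is not a protocol endpoint, so its population is the sponsor's choice.

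**What to change.** In SAP 5.3, Parameter Definitions and Secondary Analysis:

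- Define the protocol's viral and clinical relapse endpoints as proportions among the treatment-free follow-up type already defined in SAP 2.3, without the extra EOT conditions on HBV DNA and ALT.
- Use HBV DNA above 2,000 IU/mL throughout, as in the protocol and in the SAP's treatment-free failure definition.
- Define clinical relapse as in the protocol: confirmed HBV DNA above 2,000 IU/mL in association with confirmed ALT above 2 x ULN.
- Report HBV DNA rebound on NA under the existing endpoint of breakthrough during NA follow-up.
- Leave biochemical relapse as it is, shown by follow-up type.

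The cost is SAP wording and a flag that already exists. The price is a smaller denominator and a less precise estimate. The flag records meeting the completion criteria, so it matches the protocol's population but does not capture subjects who missed the criteria and took no NA under local guidelines.
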